5.7.2 Sample Size Estimation

No formal sample size estimation has been performed since this is a feasibility study. A sample size of 20 subjects was selected based upon the amount of subject exposure considered necessary in order for clinical assessments of safety, tolerability, preliminary and long-term effectiveness of the ReCell device when used for healing of full-thickness wounds treated with 1:5 meshed STSG and INTEGRA MBWM. This study does not evaluate formal hypotheses and is not prospectively powered to detect potentially clinically significant improvements in study endpoints. The results of this feasibility study may be analyzed to refine the study design for a pivotal trial.

5.7.3 Data and Statistical Analysis Plan

Due to the feasibility nature of this clinical trial, no formal statistical analysis nor interim analysis will be performed. Data collected in this study will be documented using summary tables. Quantitative variables will be summarized using descriptive statistics, including mean (and/or median), standard deviation (SD), and when appropriate minimum and maximum values. Categorical variables will be summarized by frequencies and percentages. Where appropriate, 95% confidence intervals either around the sample means or mean differences will be furnished. All data collected will be presented in subject data listings.

Power Analysis

Post hoc power analysis was conducted using G*Power 3.1 (Faul, Lang, & Buchner, 2007) for this 2 x 7 mixed design (i.e., two treatment groups x 7 waves of measurements). Given the constraints on sample size ($n = 20$), a power analysis was conducted with the intent to detect the obtained power ($1 - \beta$) given: (1) level of significance (set at $\alpha = .05$), effect size (standardized F statistic varied at .15, .2, and .25) and (3) rate of autocorrelation (average correlations of repeated measures varied at .3, .5, and .7). Even though ascertaining what constitutes a small/medium/large effect size is, in part, context and discipline-dependent, using Cohen's (2008) taxonomy of small ($F = .10$) and medium ($F = .25$) we see below that sufficient power (.80) to obtain significance for the 2 x 7 first order interaction will be obtained for a medium effect size when the autocorrelation is .5 or higher and for a slightly smaller effect size ($F = .2$) when autocorrelation approximates .7. However if the effect size approximates .15 sufficient

power will not be obtained, regardless of magnitude of autocorrelation.

AutoCorr	Effect Size	Power
0.3	0.25	0.729
0.5	0.25	0.881
0.7	0.25	0.989
0.3	0.2	0.503
0.5	0.2	0.672
0.7	0.2	0.904
0.3	0.15	0.286
0.5	0.15	0.399
0.7	0.15	0.639

Cohen (1988). *Statistical power analysis for the behavioral sciences*. (2nd Ed.). Hillsdale, NJ: Lawrence Erlbaum.

Proposed Analysis

For this 2 x 7 mixed design (i.e., two treatment groups x 7 waves of measurements) with a continuous level outcome, a two-way (completely within) repeated measures ANOVA will be performed with the overarching objective being the test of significance for the two-way treatment x time interaction (using $\alpha = .05$). If the two-way interaction is significant, simple effects analysis will be performed so as to assess at which time point significant differences for the treatment variable are obtained. Moreover, if the first order interaction is significant, trend analysis will be conducted in an effort to uncover any nonlinear patterns across time (up to polynomial $t - 1$, where $t = \text{time}$). Graphic displays will be provided so as to illuminate the nature of the findings and the between treatment trajectories.

All assumptions will be examined, including sphericity and homogeneity of variance/covariance matrices and any data anomalies (e.g., outliers) will be examined and treated accordingly. It should be kept in mind that given the small sample size ($n = 20$), there may still be substantive effects despite non-significant results, hence univariate and multivariate effect sizes will be reviewed (e.g., partial η^2).

There are many techniques beyond a mixed ANOVA approach that can more dynamically model the longitudinal nature of this design, such as multilevel modeling, generalized estimating equations, and/or latent growth curve modeling. However, those techniques will need to be deferred until a larger sample size is obtained. All analysis will be conducted using SPSS 21.0 or Stata 11.0.

Analysis Sets of ReCell Device Treatment vs. Control Comparison:

Safety Analysis Set:

The safety analysis population will include all enrolled subjects. Data will be analyzed based on treatment received. The number and percentage of subject who discontinued the study due to adverse event will be provided. Also, descriptive statistics, as

appropriate, will be provided for the following, by treatment:

- Delayed healing/non-healing of wound and donor site
- Graft loss
- Heterotopic ossification
- Infection
- Scar contracture
- Durability (i.e. abrasions/injuries at graft site due to graft fragility)
- Allergic response to trypsin
- Subject Complaint (pain and itching)
- Vital Signs
- Blood chemistries and hematology
- Safety-related issues occurring through 24 weeks after treatment, other treatment-related adverse events requiring surgical intervention prior to 12 weeks post-treatment and all serious adverse event (SAE) occurrences.

For Adverse Events (AEs), a tabulation of incidence, number of subjects and percent of subjects experiencing AEs will be provided for:

- Serious AEs
- Severity
- Expected or Unexpected
- Relationship to Study Treatment
- Body System and preferred term

A listing of all AEs along with severity, relation to treatment, date and outcome will also be provided.

Effectiveness Analysis Set:

Preliminary and long-term effectiveness data will be summarized descriptively for each of the assessment intervals by presenting the number and proportion of treatment and donor sites that achieved healing. The treated wound site will be considered healed if 95% or greater re-epithelialization has occurred by Week 6 post-treatment. Donor sites (STSG 1:5, STSG 1:1.5 and ReCell) will be considered healed when $\geq 95\%$ of the donor site has re-epithelialized by Week 4 post treatment. Both Observer and Patient Assessment scales of the POSAS, and total POSAS scores will be summarized descriptively (mean, median, standard deviation, range) at Weeks 12 and 24. The Vancouver Scar Scale (VSS) assessment tool and total VSS scores will also be summarized descriptively (mean, median, standard deviation, range) at Weeks 12 and 24. Patient satisfaction and functional outcome ratings data will be summarized in terms of counts, percentages and other descriptive statistics.

Histology Analysis

Histological analyses will be performed on punch biopsies of ReCell-treated and control sites for Week 2, 4 and 12 and also of the pre-treatment biopsies taken from the INTEGRA™ MBWM treated wound site and adjacent normal skin. This biopsy of

normal skin serves as the control control for all other biopsies. At each assessment interval, histological parameters from both ReCell-treated and control biopsies will be compared to the same parameters as measured in normal skin. Data will be summarized descriptively.

Cell Suspension Preparation/Application Parameters Analysis

Data concerning biopsy size and thickness, wound size, and ReCell cell suspension application (e.g., volume and details for application) will be documented on the eCRF. Data will be summarized using descriptive statistics.

Demographic Data Analysis

Tabulation of demographic data will be tabulated by age, gender and race/ethnicity.

Study Termination Analysis

The following analysis will be provided pertaining to Study Termination:

- Number and percent of subjects who completed the study
- Frequency of premature termination reasons
- A listing of all subjects who were prematurely terminated from the study along with the reason and date of early termination

The following will be considered as major protocol deviations:

- Major inclusionary/exclusionary deviations
- Missed visits/assessments such that a determination of healing status at both wound sites and ReCell donor site cannot be determined
- Significant protocol non-compliance that may confound evaluation of healing (e.g. use of inappropriate primary dressing)

Any significant deviations to the statistical analysis plan will be addressed in the final report for this study.

Randomization:

Allocation of treatments to the 2 defined wound regions at the INTEGRA™ MBWM treated wound sites will be done at random, using a computer generated randomization table provided by Glaser Consulting. Wound regions will initially be labeled “A” region and “B” region by the surgeon, and then an envelope will be opened which will indicate which treatment (ReCell or control) to assign to “A” region and which treatment to assign to “B” region. Randomization envelopes containing treatment region allocation will be opened in chronological order corresponding to subject enrollment.

Example Randomization Table

SUBJECT #	TREATMENT ASSIGNMENT
DERM- 001	A Region (ReCell) B Region (Control)
DERM- 002	A Region (ReCell) B Region (Control)

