5. PLAN

5.1 Study Design

This is a prospective, single-center, randomized within-patient controlled feasibility study to evaluate safety, tolerability, preliminary and long-term effectiveness of the ReCell device when used in combination with STSG mesh for healing of full-thickness wounds previously treated successfully with INTEGRA™ MBWM. Due to the nature of the study, only patients whose wounds have been treated with INTEGRA MBWM as part of their standard of care will qualify for study participation. The local standard of care is considered the application of INTEGRA MBWM after the wound is amenable. Amenable being no evidence of evolving necrosis, clean and devoid of infection. The INTEGRA is allowed to mature until it takes (adheres) to the underlying tissue, which takes 2 to 4 weeks until the wound is amenable for split thickness skin grafting. Therefore, before consenting and enrollment into the study, the wound area to be studied will be treated first with INTEGRA™ MBWM then be allowed to heal for approximately two to four weeks (consistent with standard of care), at which time an assessment will be made to

determine if a viable granulation layer suitable for second stage grafting is present.
(Note: At this time the patient will complete the consent process as described below in Section 5.5.2).

The basic study design has the following characteristics:

- Each subject will serve as his/her own control
- After INTEGRA™ MBWM treatment (and once viable granulation is present), the study wound area will be divided into two regions within itself. Study treatment to each of the two regions will be assigned by randomization. Subjects will be blinded to treatment area assignments to avoid bias
- Each subject will be treated with meshed STSG over both the control and ReCell regions of the Integra-treated wound. The control area will have standard 1:1.5 meshing (only) STSG, and the experimental area will have 1:5 meshing STSG plus application of ReCell (ReCell will be applied over the 1:5 meshed STSG).

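### The power table matches a two-independent-group calculation, while the trial and its planned ANOVA are completely within-subject; at the table's own inputs it understates power by up to 34 points

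*Combined protocol and SAP*

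**What the plan says.** The Power Analysis paragraph of section 5.7.3 states: "Post hoc power analysis was conducted using G*Power 3.1", and describes the calculation as being "for this 2 x 7 mixed design (i.e., two treatment groups x 7 waves of measurements"). Sample size is fixed at 20 and alpha at .05. The other inputs are "effect size (standardized F statistic varied at .15, .2, and .25") and an average correlation among repeated measures of .3, .5 or .7. The tested effect is the treatment-by-time interaction, with .80 as the target.

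The text concludes that f = .25 reaches the target once the correlation is .5 or more, and that f = .20 reaches it when the correlation is about .7. For an effect near .15 it says that sufficient "power will not be obtained, regardless of magnitude of autocorrelation".

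The Proposed Analysis paragraph repeats the mixed-design label but then says that "a two-way (completely within) repeated measures ANOVA will be performed". Section 5.1 fixes the design: "Each subject will serve as his/her own control".

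**The concern.** A mixed design with two treatment groups has different subjects in each group. This trial has none: both treatments are applied in every subject, so 20 subjects give 20 × 2 × 7 = 280 observations. Two independent groups totalling 20 give 20 × 7 = 140. If the table came from the two-group formula, it describes a test that will not be run, and its powers and the thresholds read from them do not describe the planned test.

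At stake is whether a reader can rely on the plan's statements about which effects the interaction test can detect. The Proposed Analysis makes that test its main objective. The mixed, two-group label could also lead an analyst to set up the wrong model.

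**Working it through.** **Inputs.** From section 5.7.3: n = 20, 7 waves, alpha = .05, f = .15/.20/.25, r = .3/.5/.7. From section 5.1 and the Proposed Analysis: both factors within subject. Not stated: the sphericity epsilon, the basis on which f is defined, the correlation between regions, and the number of complete pairs. Power is the upper tail of the noncentral F distribution with noncentrality λ.

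**1. Reproduce the printed table.** For the within-between interaction with two independent groups, total N = 20, 7 waves and epsilon = 1:

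- λ = f² × 20 × 7/(1 − r) = 140 f²/(1 − r)
- df = (2 − 1)(7 − 1) = 6 and (20 − 2)(7 − 1) = 108
- Example, f = .20 and r = .3: λ = .04 × 140/.7 = 8.0, power .503 (printed .503)

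The nine results are .7295, .8812, .9887 (f = .25), .5031, .6729, .9038 (f = .20) and .2862, .3994, .6393 (f = .15). Eight agree with the table to the third decimal; the ninth is .6729 against .672. A total of 40, or 6 or 8 waves, does not reproduce the table.

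**2. Same inputs, planned analysis.** For 20 subjects with both regions at 7 visits and epsilon = 1:

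- λ = f² × 20 × 14/(1 − r) = 280 f²/(1 − r)
- df = 6 and (20 − 1)(7 − 1) = 114
- Example, f = .20 and r = .3: λ = .04 × 280/.7 = 16.0, power .847

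**3. Allow for nonsphericity.** λ and both df are multiplied by epsilon. As an illustration, a serial correlation of .9 per week over Weeks 1, 2, 3, 4, 6, 12 and 24 gives epsilon 0.50, with average correlation .51.

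| f | r | Printed | Within, epsilon 1 | Within, epsilon .75 | Within, epsilon .5 |
|---|---|---|---|---|---|
| .25 | .3 | .729 | .973 | .930 | .829 |
| .25 | .5 | .881 | .997 | .986 | .939 |
| .25 | .7 | .989 | >.999 | >.999 | .996 |
| .20 | .3 | .503 | .847 | .757 | .621 |
| .20 | .5 | .672 | .953 | .897 | .781 |
| .20 | .7 | .904 | .998 | .991 | .953 |
| .15 | .3 | .286 | .562 | .476 | .375 |
| .15 | .5 | .399 | .735 | .637 | .509 |
| .15 | .7 | .639 | .939 | .875 | .752 |

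The largest gap at epsilon 1 is .847 − .503 = .344. Simulation of the within-subject design (10,000 trials per cell) agrees: .842 for f = .20, r = .3, and .941 for f = .15, r = .7.

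**4. The statement on f = .15.** Under the two-group formula itself, r = .8 gives λ = .0225 × 140/.2 = 15.75 and power .839; r = .9 gives λ = 31.5 and power .993.

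**5. Fewer complete pairs.** With 16 complete pairs (an assumption), λ = f² × 16 × 14 × epsilon/(1 − r), and df = 6 epsilon and 90 epsilon. At epsilon .5, power for r = .3/.5/.7 is .720/.866/.982 (f = .25), .508/.667/.889 (f = .20) and .300/.410/.636 (f = .15).

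**The case against.** **Nothing rests on the table.** Section 5.7.2 says that no formal sample size estimation was made, bases n = 20 on subject exposure and disclaims prospective powering. The primary outcomes are safety and tolerability, summarized descriptively. The planned ANOVA is already the within-subject one, and the table errs on the cautious side. All of this stands and limits the severity.

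**The conclusions may survive.** A reader might infer that every conclusion drawn from the table is wrong. The figures do not support that. At epsilon = 0.5, f = .15 stays below .80 in all three tabulated cells, and f = .20 passes only at r = .7, as the text says. Only the f = .25 threshold moves, since r = .3 already gives .829. But this needs strong nonsphericity: at epsilon .75, f = .20 passes at r = .5 and f = .15 passes at r = .7. The printed table makes no such allowance.

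**The corrected powers may flatter.** They assume 20 complete pairs at all seven visits, while treated subjects who withdraw are not replaced (section 5.5.4, Subject Discontinuation and/or Withdrawal). With 16 pairs and epsilon .5, the results lie within about .015 of every printed entry. That agreement depends on two chosen assumptions and does not justify the printed calculation, but attrition must be shown.

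**Another reading of the inputs.** If f and r described within-patient differences, 20 subjects with 7 measures would give powers close to the table (largest gap .0024). That version matches only one of nine cells to the third decimal, and the text speaks of two treatment groups, not of differences.

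**The pivotal trial.** A reader might also infer that these powers will be carried into a pivotal design. Section 5.7.2 says only that the study's results may be used to refine one; it does not mention this table.

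**Conclusion.** The concern holds, with moderate severity. The printed powers are those of a two-independent-group interaction test with epsilon = 1. The documents do not state 10 per group; it is inferred from the numerical match. For the completely within-subject test that is planned, the table understates power by up to 34 points at its own inputs.

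This size assumes that f and r refer to the raw measurements, that there are 20 complete pairs, that epsilon = 1, and that the correlation between regions is the same at equal and at different visits. A higher same-visit correlation would raise power further; nonsphericity and attrition would lower it.

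The text's conclusions for f = .20 and f = .15 hold within the tabulated correlations only under strong nonsphericity, such as epsilon 0.5. The statement that f = .15 fails at any correlation is false under either formula at epsilon = 1. None of this shows that n = 20 is too small or should change.

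**What to change.** In section 5.7.3:

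1. Replace the table with the completely within-subject 2 × 7 interaction calculation. State the effect-size basis, the assumed correlation between regions, epsilon (1 and about 0.5) and the number of complete pairs (20 and a lower number for attrition).
2. Delete the statement that f = .15 fails at any correlation, or limit it to the tabulated correlations and stated assumptions. Rewrite the other thresholds from the new table.
3. Correct the mixed-design and two-treatment-group labels in both the Power Analysis and Proposed Analysis paragraphs.

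The cost is one re-run of the calculation and a wording change. Sample size, visits and trial conduct are unaffected.

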A subject may withdraw consent and discontinue participation in the study at any time and for any reason without penalty, if he/she wishes to do so. The investigator may also withdraw a subject if continuing participation is believed to be harmful to the subject’s well-being or in the event of protocol violations, non-compliance (i.e. loss to follow-up), the need to initiate care contraindicated to study procedures and/or requirements, pregnancy, serious inter-current illness and if the study is cancelled due to other administrative reasons and/or unanticipated circumstances by the Sponsor of this study or the FDA. Additionally, the subject’s participation may be stopped without their consent if the military mission requires it or if the individual loses his/her DoD healthcare beneficiary status.

If the subject’s participation is stopped, the investigator will notify the subject and provide reason for doing so in person, by mail, email and/or telephone.

In the event that the subject withdraws and/or is withdrawn from the study before the completion of the Week 24 post-treatment assessment, he/she will be asked to come to the clinic for a final assessment of safety evaluations. If a subject withdraws before study completion, the reason for discontinuation will be captured on the appropriate eCRF page. Additionally, any data collected up until the time of subject withdrawal will be included in the final study analysis. (*Please see section 5.5.7 for additional information pertaining to biological specimens/withdrawal*)

Subjects who are withdrawn will not be replaced if they have received study treatment.

Additional Information:

Patient and Observer Scar Assessment Scale (POSAS)

The standard and comprehensive Patient and Observer Scar Assessment Scale (POSAS) [Draaijers LJ, et al., 2004] will be employed in this study, as a standard tool for capturing both the subject’s and two independent observer’s assessment of the scar post-treatment

[Idriss N, 2009]. Although many methods of rating scars exist, little consensus exists to dictate which method is optimal [Fearmonti R, et al., 2010, Durani P, et al., 2009]. Objective measures may be useful for evaluating a particular characteristic (e.g. color or elasticity), but these do not satisfactorily convey overall, clinically-relevant information about the scar as a whole [Brusselaers N, et al., 2010].

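### The only planned significance test asks whether the ReCell-control difference changes over time, so no planned test targets a difference present at Week 1 and sustained

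*Combined protocol and SAP*

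**What the plan says.** Under Proposed Analysis, Section 5.7.3 describes the design as "two treatment groups x 7 waves of measurements" and plans a completely within-subject repeated-measures ANOVA for a continuous outcome, "with the overarching objective being the test of significance for the two-way treatment x time interaction", at alpha 0.05. The outcome is not named. Both follow-up steps are conditional: "If the two-way interaction is significant, simple effects analysis will be performed", to find the visits at which the treatments differ, and "if the first order interaction is significant, trend analysis will be conducted". No use is described for the treatment main effect, and the power table in the same section concerns the interaction alone.

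Several items in 5.7.3 do not depend on the interaction: 95% confidence intervals for means or mean differences where suitable, effect sizes examined even when tests are not significant, graphs of the trajectories, effectiveness summaries at each assessment interval, and safety tables by treatment.

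Section 5.7.2 and the opening of 5.7.3 say that the study tests no formal hypotheses and will have no formal statistical analysis.

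On incomplete records, Section 5.5.4 (Subject Discontinuation and/or Withdrawal) says that "any data collected up until the time of subject withdrawal will be included in the final study analysis". Section 5.7.3 gives no rule for a missed visit in the ANOVA. Of multilevel models, generalized estimating equations and growth curves it says that "those techniques will need to be deferred until a larger sample size is obtained".

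**The concern.** Most of the predictions in Section 3 are about level: safety, healing, scar, function and satisfaction in the ReCell region should be no worse than in the control region. The interaction asks something else, namely whether the difference between regions varies across visits.

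With a pre-treatment wave for each region, a treatment effect would appear as divergence from baseline and the interaction would pick it up. There is no such wave. The seven visits are Weeks 1, 2, 3, 4, 6, 12 and 24 after treatment. Screening pain and itch are recorded for the wound as a whole, before regions A and B are marked at surgery. A difference that is established by Week 1 and persists is plausible, and it leaves the interaction null.

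The ANOVA would then give a non-significant result and the planned follow-up tests would not be run. Section 5.7.2 says the results may be used to refine a pivotal trial. For that purpose the size of the paired difference matters more than whether it changes over time.

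**Working it through.** **1. The plan's own power table.** Inputs from 5.7.3: N = 20, m = 7 visits, alpha 0.05, effect size f = 0.15, 0.20 or 0.25, correlation rho = 0.3, 0.5 or 0.7. Noncentral F with df1 = 6, df2 = (20 − 2) × 6 = 108 and lambda = f² × N × m / (1 − rho). For f = 0.25 and rho = 0.5:

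lambda = 0.0625 × 20 × 7 / 0.5 = 17.5, power 0.881 (stated 0.881).

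All nine entries reproduce to within 0.001. Using the fully within-subject df2 = 19 × 6 = 114 changes them by at most 0.002. The table is arithmetically right, but it describes the interaction only.

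**2. The interaction under a constant difference.** For subject i at visit j let D(i,j) be ReCell minus control. The interaction F is the one-way repeated-measures F for visit computed on D. Its numerator uses the visit means of D minus their grand mean. If D(i,j) = delta + subject term + error, delta cancels and lambda = 0. Under sphericity the rejection rate is then alpha, whatever delta is. In simulations of 20,000 trials per setting, with several correlation structures and differences from 0.2 to 0.8 SD, the interaction rejected in 4.6% to 5.3% of trials.

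**3. A direct paired test under the same conditions.** Average D over the seven visits for each subject and apply a two-sided paired t test with 19 df and noncentrality dz × √20. Here dz is the mean of the averaged difference divided by its between-subject SD.

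| dz | Power, paired test | Power, interaction |
|---|---|---|
| 0.4 | 0.40 | about 0.05 |
| 0.5 | 0.57 | about 0.05 |
| 0.6 | 0.72 | about 0.05 |
| 0.8 | 0.92 | about 0.05 |
| 1.0 | 0.99 | about 0.05 |

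Power of 80% is reached at dz of about 0.66.

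The documents give no variance components, so the dz that matches a given raw difference is an assumption. For a constant 0.5 SD difference, with total variance 1 and error variance 0.5, dz = 0.5 / √(2 × (b + 0.5/7)), where b is the subject-by-region variance:

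- b = 0.40: dz = 0.51, simulated power 0.58
- b = 0.25: dz = 0.62, simulated power 0.75
- b = 0.20: dz = 0.68, simulated power 0.82
- b = 0 (common correlation 0.5): dz = 1.32, simulated power above 0.99

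**4. Missed visits, as a sensitivity only.** The documents give neither a complete-case rule nor a missing rate. If only subjects with all visits were analysed, and visits were missed independently at rate p, the expected number kept is 20 × (1 − p)^7. That is 17.4 at 2%, 14.0 at 5% and 9.6 at 10%. Interaction power at f = 0.25 and rho = 0.5 would fall from 0.881 to about 0.71 with 14 subjects and about 0.51 with 10. Clustered losses cost less. At 5%, 0.05 × 140 = 7 subject-visits are missed. If these came from two withdrawals, 18 subjects would remain, with power about 0.84.

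**The case against.** The strongest reply is that this is a feasibility study that disclaims formal hypotheses, so it cannot be faulted for lacking a test. It also already promises ungated descriptions and intervals for mean differences, and the interaction suits its hypothesis of faster healing (Sections 4.1 and 4.3), which is about trajectory. Much of this stands. It limits the severity, and it justifies keeping the interaction. It does not remove the point. Proposed Analysis still sets an alpha-level test with conditional follow-ups, which conflicts with the disclaimers. The plan also never says which difference, outcome or visit will receive an interval.

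Three stronger readings are tempting, and the documents do not support them.

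- *A constant difference could not be reported at all.* The confidence intervals, effect sizes, graphs and summaries are ungated, so it could be estimated and shown. What is missing is a planned test or a named contrast aimed at it.
- *Consistent harm would be hidden.* Most primary safety outcomes are categorical (graft loss, infection, contracture and others) and are tabulated by treatment with no gate. The ANOVA needs a continuous region-level outcome at seven visits, and in the schedule of assessments that is in practice the patient POSAS. The Vancouver scale, observer POSAS, functional rating and satisfaction are collected only at Weeks 12 and 24.
- *The ANOVA drops anyone with a missed visit, contradicting 5.5.4.* No such rule is stated. Two packages are allowed without fixing the implementation, and the commitment in 5.5.4 could be met through summaries and listings. Appendix H, which covers statistical management, is listed but its content is not in the documents, so a rule may be there.

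**Conclusion.** The point holds for the continuous outcome that the 2 × 7 ANOVA can use. The only alpha-level test is the interaction, both follow-up significance steps depend on it, and it rejects at about 5% under a constant difference of any size. A paired test of the average difference with 20 pairs would have 57% to 99% power for dz between 0.5 and 1.0. The 5% figure assumes sphericity and a difference that is truly flat from Week 1. If the regions diverge or converge over time, the interaction does have power, as the plan's own table shows.

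The missing-visit issue is secondary. The plan does not say how the ANOVA will honour the commitment to use data up to withdrawal, and any figure for lost subjects rests on assumed rates. Overall this should be fixed because it is cheap and changes what the trial can conclude. It does not invalidate a feasibility study whose main outputs are descriptive.

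**What to change.** In Section 5.7.3:

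- Name the outcome for the 2 × 7 analysis.
- Specify the within-subject ReCell-minus-control difference, averaged over visits and at each visit, with 95% confidence intervals reported whether or not the interaction is significant.
- Keep the interaction as a secondary description of how the difference evolves.
- Compute the differences from all observed visits, by paired t intervals at each visit or by a simple mixed model, and state the rule for missed visits so that the commitment in 5.5.4 is met.
- Reconcile Proposed Analysis with the statements in 5.7.2 and at the start of 5.7.3 that no formal hypotheses or formal analysis are planned.

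The cost is SAP wording and a little more analysis work. No added subjects, visits or measurements are needed. If a mixed model is used, it brings a missing-at-random assumption, which should be stated.

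### After a non-significant test the plan looks for substantive effects in uncorrected partial eta-squared, which at n = 20 averages 0.05 (univariate) and 0.30 (multivariate) when there is no effect

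*Combined protocol and SAP*

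**What the plan says.** Under Proposed Analysis in Section 5.7.3, for a continuous outcome at 7 visits, "a two-way (completely within) repeated measures ANOVA will be performed", with the treatment-by-time interaction tested at the .05 level. The plan then turns to non-significant results. Because the sample is small, "there may still be substantive effects despite non-significant results, hence univariate and multivariate effect sizes will be reviewed", with partial eta-squared as the example. It does not say what size would count as substantive, and it provides no bias correction or interval for these effect sizes.

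Two other parts of Section 5.7.3 bear on this. The opening paragraph says that, where suitable, "95% confidence intervals either around the sample means or mean differences will be furnished". The Power Analysis paragraph labels f = .10 small and f = .25 medium, remarks that such labels depend partly on context and discipline, and uses f = .15, .20 and .25 as inputs to a power table. It does not link these values to the later review of effect sizes.

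Section 5.7.2 says that the study tests no formal hypotheses and that its results may help to refine a pivotal design.

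**The concern.** Sample partial eta-squared cannot be negative, and its expected value under no effect is df1/(df1 + df2). With 6 interaction degrees of freedom and 20 subjects that value is well above zero, especially in the multivariate form. A reader told to look for substantive effects after a null test will therefore see a positive number every time, and in the multivariate output usually one that looks large. The number also does not say whether ReCell or control did better.

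The situation is likely to arise. The plan's own table gives power of only 0.286 to 0.639 at f = .15. At stake is how a null result is described, and what is carried into thinking about a pivotal trial.

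**Working it through.** **Inputs (Section 5.7.3).** n = 20; a 2 x 7 layout ("two treatment groups x 7 waves of measurements"); an analysis completely within subjects; alpha .05; "average correlations of repeated measures varied at .3, .5, and .7". The plan does not name the outcome. One that fits 7 visits is the patient part of the POSAS, collected at every post-treatment visit according to the schedule of procedures.

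**Step 1: reproduce the power table.** Use a noncentral F with lambda = f² x N x m / (1 - rho), N = 20, m = 7, and 6 and 108 df. At f = .25, lambda = 8.75/(1 - rho), which is 12.5, 17.5 and 29.17 at rho = .3, .5 and .7. The powers are 0.7295, 0.8812 and 0.9887, against 0.729, 0.881 and 0.989 in the plan. All nine entries agree within 0.001. With 6 and 114 df they agree to about 0.002. If f = .25 were instead the f that corresponds directly to partial eta-squared, lambda would be 0.0625 x 108 = 6.75 and power 0.427 at every correlation. The table's f is therefore on a different scale.

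**Step 2: behaviour with no effect.** For a fully within-subject interaction the univariate df are 6 and 6 x 19 = 114, and the multivariate df are 6 and 20 - 6 = 14. Under no effect, partial eta-squared follows Beta(df1/2, df2/2).
- Univariate mean: 6/120 = 0.05. A result is significant above 0.103.
- Multivariate mean: 6/20 = 0.30, median 0.29. A result is significant only above 0.55, so any value up to about 0.55 is non-significant.
- With an assumed 16 complete subjects the means are 6/96 = 0.0625 and 6/16 = 0.375.

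**Step 3: an assumed cut-off from the usual conversion.** Partial eta-squared = f²/(1 + f²) = 0.0625/1.0625 = 0.0588.
- Univariate: P(F(6,114) > 1.1875) = 0.318. Given non-significance, (0.318 - 0.05)/0.95 = 0.282.
- Multivariate: P(F(6,14) > 0.1458) = 0.987. Given non-significance, (0.987 - 0.05)/0.95 = 0.986.

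Simulation of 40,000 trials per setting gives 31.3% and 98.6% over all trials under compound symmetry, and 30.6% to 30.8% and 98.7% under AR(1) with parameter .5 or .7. The conditional univariate figure depends somewhat on sphericity. Under AR(1) it is 24% to 25% with the uncorrected F test and 27% to 28% with a Greenhouse-Geisser correction.

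**Step 4: the same f on the power table's scale.** The benchmark is lambda/(lambda + 114) univariate and lambda/(lambda + 20) multivariate.

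| rho | Univariate benchmark | Exceeded, no effect | Multivariate benchmark | Exceeded, no effect |
|---|---|---|---|---|
| .3 | 0.099 | 6.05% | 0.385 | 26.2% |
| .5 | 0.133 | 1.1% | 0.467 | 12.7% |
| .7 | 0.204 | 0.02% | 0.593 | 2.8% |

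These count all no-effect trials. Among non-significant ones the univariate figures are (0.0605 - 0.05)/0.95 = 1.1%, then zero, because 0.133 and 0.204 lie above the significance threshold of 0.103. The multivariate figures are (0.262 - 0.05)/0.95 = 22%, (0.127 - 0.05)/0.95 = 8%, and zero, because 0.593 lies above 0.55.

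**The case against.** The strongest reply is that the plan only reviews effect sizes. It contains no rule that declares an effect, and partial eta-squared is just an example. The study is a feasibility study with safety and tolerability as primary outcomes, and looking at effect sizes in such a study is common. The plan already foresees confidence intervals for mean differences, graphs of the treatment trajectories and descriptive summaries, which are signed and in outcome units.

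Much of this stands. A reader might infer that f = .25 is the plan's own threshold for the review, and that noise would pass it in roughly a third (univariate) or nearly all (multivariate) of trials. The documents do not support that: f = .25 appears only as a power input, and on the scale of that table the no-effect exceedance is far smaller. Nor does the multivariate figure survive the change of scale. A cut-off of 0.14 applied to the multivariate statistic gives 88%, but that sets a univariate-scale value against a multivariate statistic. A reader might also infer that partial eta-squared will be used to size a pivotal trial. Section 5.7.2 says only that results may be used to refine its design.

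The reply does not remove the point. The intervals are planned only where suitable, and nothing ties them to each visit or to the reading of a non-significant test. For that situation the plan names effect sizes, with no rule for converting or judging them.

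**Conclusion.** The concern holds as a weakness in how null results would be interpreted. It is not evidence that the plan would declare false effects at a known rate. What needs no benchmark is firm: with 20 complete subjects, normal data and no effect, partial eta-squared for the interaction averages 0.05 univariate (under sphericity) and 0.30 multivariate. A non-significant multivariate value can reach about 0.55, and the statistic is unsigned. Fewer complete subjects make this worse.

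How often noise would look substantive depends on a yardstick that the plan does not give. Among non-significant no-effect trials it is about 28% and 99% under an assumed cut-off of 0.059. On the power table's scale it is 0.02% to 6% and 3% to 26% over all no-effect trials. All figures take multivariate to mean the multivariate test of the treatment-by-time interaction. The change is a cheap improvement and worth making.

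**What to change.** Replace the sentence on effect sizes after non-significant results with: *Whatever the p-value, the paired ReCell minus control mean difference with its 95% CI will be reported at each visit in the units of the outcome, and statements on size and direction will rest on these.*

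If a standardised effect is still wanted, use a bias-corrected one (partial omega-squared) with its CI, and drop the multivariate partial eta-squared.

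The cost is one sentence in the SAP and no new data. It makes firm an interval that the plan already foresees. The downside is that small effects will look less favourable.
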